#### 8.4 SECONDARY OUTCOME STATISTICS

Evaluation of feasibility that a (Likert) scale can be applied for Medipin in relation to degree of neuropathy, as opposed to standard yes/no quantification and no sensation/dull sensation/sharp sensation distribution. For this, descriptive statistics will be used to present how results are distributed amongst these three outcome modalities. Mann-Whitney U-test will be used to compare median 10-point score between those with present and absent DN respectively (ie yes/no groups), to determine if the median value differs. Similarly, Kruskall-Wallis test will be used to compare median score between the three groups of no sensation/dull sensation/sharp sensation.

Concordance between Medipin and 10g monofilament test results. The binary outcome , DN present or absent, will be used to conduct concordance and distribution comparisons. Cohen's Kappa value will be calculated to assess level of concordance. McNemar's test for paired data will be used to compare distribution of outcomes between Medipin and each 10g monofilament procedure outcome.

Relative performance/concordance achieved with 10g monofilament depending on number of tests and locations included in the assessment. As above for concordance measurement between Medipin outcome and respective 10g monofilament outcomes, the same test is conducted to compare the two different 10g monofilament diagnostic test procedures.

The patient's age, years of diabetes, smoking status, blood pressure medication and diabetes medication, foot malformations, general quality of life (EQ-5Q-DL), and MNSI symptom questionnaire score are primarily used to define the cohort on which the DN screening has been conducted. Parameters collated at the clinic visit will be recorded and presented in a tabulated format. No identifiable data will be presented, only averages and totals.

However, binary logistic regression may be applied to evaluate if any parameters are associated with Medipin positive tests, with the the Medipin result being the dependent variable. Likewise, this regression analysis can also be used with either of the monofilament test outcomes as the dependent. This will then allow comparison of variables associated with small fibre and large fibre screening. This type of analysis may only be feasible with the potential larger sample size outlined in Section 8.2 of this protocol. Odds ratios (logistic) will be expressed as Beta with 95% confidence intervals.

Analysis will be performed on a per protocol basis since there will be no loss to follow-up, and inferential statistics will be performed on pooled data. Data will first be collated in Microsoft Excel, followed by analyses performed using SPSS v24.

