#### 8.3 PRIMARY OUTCOME STATISTICS

The Medipin result and monofilament result (either dorsal or plantar outcome) will be presented with descriptive statistics to show percentage of patients with LOPS / DN.

Test	DN Absent	DN Present
10g Monofilament test plantar side, five	Score of 9 or 10 (out of 10)	Score of 8 or lower
plantar locations on both left and right		
foot		
10g Monofilament test: four applications	Score of 3.5 or higher (out of 8).	Score of 3 or lower
on dorsal side of hallux, proximal to	Recognising that score 3.5 to 5	
toenail, on both left and right foot	considered elevated risk of DN in	
	original reference article.	
Medipin test: one application on dorsal	Sensation in both feet (either 'dull'	No sensation in one or
side of hallux, proximal to toenail, on	or 'sharp' sensation, and score of	both feet
both left and right foot	above 0 out of 10)	

Table 6, Definition and score cut-offs for different DN tests (based on published papers).

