## Appendix 1, Case Report Form

Patient Code:

MANDARIN-.....

Researcher completing form: .....

item	outcome	
Patient visit date		
Patient age	Years	
Patient height / weight / BMI	Height (m) Weight (kg) BMI	
Year type II diabetes diagnosed		
Smoking status	Never Ex-smoker Current smoker	
Peripheral Arterial Disease (PAD) recorded in notes	No Yes	
Patient on antihypertensive medication?	No Yes (if yes, which medication?)	
Foot and/or toe malformation recorded in notes	No Yes If yes: - Toes - Foot - Both toes and foot	
Current medication for diabetes	Biguanides (Metformin) Alpha-glucosidase inhibitors (eg acarbose miglitol (Glyset))	
	Dipeptidyl peptidase-4 (DPP-4) inhibitors (eg alogliptin (Nesina), linagliptin (Tradjenta), saxagliptin (Onglyza), sitagliptin (Januvia)	
	Glucagon-like peptide-1 receptor agonists (GLP-1 receptor agonists) (eg dulaglutide (Trulicity), exenatide (Byetta), liraglutide (Saxenda, Victoza) lixisenatide (Adylyxin), semaglutide (Ozempic), tirzepatide (Mounjaro)	
	Meglitinides (eg nateglinide (Starlix), repaglinide (Prandin))	
	Sodium-glucose transporter (SGLT) 2 inhibitors (eg canagliflozin (Invokana), dapagliflozin (Farxiga), empagliflozin (Jardiance), ertugliflozin (Steglatro)	
	Sulfonylureas (eg glimepiride (Amaryl), gliclazide Glipizide, glyburide (Glynase), glyburide-metformin)	

	Thiazolidinediones (eg rosiglitazone, pioglitazone-alogliptin (Oseni))	
	Insulin 
 
rapid- or short-acting insulin.
 
mixed insulin.
 
long-acting insulin.
 
	
Medipin outcome (dorsal, hallux)	Left foot (patient's left foot)	
	
 
Sharp sensation
 
Dull sensation
 
Absent sensation
 
Score if sensation felt (5 being forearm reference score):
 
	
	$\bigcirc 0 & 1 & 2 & 3 & 4 & 5 & 6 & 7 & 8 & 9 & 10 \\ \bigcirc \bigcirc \bigcirc & \bigcirc \bigcirc \bigcirc & \bigcirc \bigcirc \bigcirc & \bigcirc \bigcirc \bigcirc & \bigcirc \bigcirc & \bigcirc \bigcirc & 0 & 0$	
	Right foot 
 
Sharp sensation
 
Dull sensation
 
Absent sensation
 
Score if sensation felt (5 being forearm reference score):
 
	
	$\begin{array}{ c c c c c c c c c c c c c c c c c c c$	
Monofilament 10g (dorsal, hallux)	
 
Left foot (1st application)
 
Present sensation (same or more as forearm)
 
Present sensation (substantially less than forearm)
 
Absent sensation
 
	

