# Appendix 4, Michigan Neuropathy Screening Instrument symptom questionnaire

#### MNSI symptom questionnaire

1. Are your legs and/or feet numb?	Yes / No
2. Do you ever have any burning pain in your legs and/or feet?	Yes / No
3. Are your feet too sensitive to touch?	Yes / No
4. Do you get muscle cramps in your legs and/or feet?	Yes / No
5. Do you ever have any prickling feelings in your legs or feet?	Yes / No
6. Does it hurt when the bed covers touch your skin?	Yes / No
7. When you get into the bath or shower, can you tell hot water from cold water?	Yes / No
8. Have you ever had an open sore (ulcer) on your foot?	Yes / No
9. Has your doctor ever told you that you have diabetic neuropathy?	Yes / No
10. Do you feel weak all over most of the time?	Yes / No
11. Are your symptoms worse at night?	Yes / No
12. Do your legs hurt when you walk?	Yes / No
13. Are you able to sense your feet when you walk?	Yes / No
14. Is the skin on your feet so dry that it cracks open?	Yes / No
15. Have you ever had a (toe/foot/leg) amputation?	Yes / No

Total number of reported symptoms based on composite score of MNSI symptom questionnaire "yes" responses, with questions 7 and 13 reverse-scored.

From Ylitalo et al (2013):

Questions 1, 8, 13, and 15 are considered indicators of large fibre nerve dysfunction.

Questions 2, 3, 5, 6, 7, and 14 are considered indicators of small fibre nerve dysfunction

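### Section 8.4 tests the Medipin 10-point score against groups formed from the same Medipin answer, so the tests cannot show that the scale grades neuropathy

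*Protocol*

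**What the plan says.** The secondary objective is whether a graded "scale can be applied for Medipin in relation to degree of neuropathy, as opposed to standard yes/no quantification" (section 8.4). Three methods follow:

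- a descriptive account of how results fall across the yes/no, three-category and 10-point readings;
- a "Mann-Whitney U-test will be used to compare median 10-point score between those with present and absent DN respectively (ie yes/no groups");
- a Kruskal-Wallis test to "compare median score between the three groups of no sensation/dull sensation/sharp sensation".

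The groups are defined in Table 6 (section 8.3). DN present on Medipin begins "No sensation in one or" and continues to both feet. DN absent needs dull or sharp sensation in both feet and adds a condition on the score: "or 'sharp' sensation, and score of" above 0 out of 10.

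Under step 4 of the Medipin test (section 5.3), one application per foot yields both the none/dull/sharp answer and the score. The Case Report Form in Appendix 1 asks, for each foot, "Score if sensation felt (5 being forearm reference score"), on a scale printed from 0 to 10.

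Section 8.4 sets no test of the 10-point score against the monofilament or the MNSI. The optional logistic regression uses the binary Medipin result, not the score.

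**The concern.** A test of whether a score tracks the degree of neuropathy needs a grouping that the score did not help to form. Here both come from one answer to one stimulus, and the score is part of the rule for DN absent. A patient who feels nothing has either a 0 or no score, and neither carries information about grading.

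At stake is how the result would be read. A very small p-value could be reported as support for the graded scale when random numbers would have produced it.

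A related gap reaches the primary outcome. The form allows a foot to be felt yet scored 0. Such a patient fails the DN-absent rule because the score is not above 0, and fails the DN-present rule because there is sensation.

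**Working it through.** **Inputs.** N = 139, extended N = 552 and 10% prevalence are from section 8.2; group definitions from Table 6; recording rule from the Case Report Form.

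**The plan's own figure.** n0 = 1.96² × 0.10 × 0.90 / 0.05² = 138.29. With the finite-population correction for 160,000 this is 138.17, rounded up to 139. At 2.5% precision: 553.17, corrected to 551.27, rounded up to 552. Both reproduce. The protocol gives no figure for the two tests examined here.

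**Absent coded 0, by hand.** 10% of 139 is about 14 DN-present patients, leaving 125. If all 14 have 0 and everyone else is above 0, separation is complete whatever the other scores are:

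- mean of U = 14 × 125 / 2 = 875, so U deviates from its mean by 875;
- SD = √(14 × 125 × 140 / 12) = 142.9, ignoring ties;
- z = 875 / 142.9 = 6.12, two-sided p ≈ 9 × 10⁻¹⁰.

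With random integers 1-10 for the 125 and ties handled, the largest Mann-Whitney p in 3,000 runs was 7.9 × 10⁻¹⁰. The largest Kruskal-Wallis p (14 none, 38 dull, 87 sharp) was about 6 × 10⁻⁹. Two patients at 0 among 139 are enough (largest p 0.015); one is not (0.086).

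**Absent coded 0, allowing for one-foot cases.** Assumptions not in the protocol: two-sided 0.05; felt feet 70% sharp and 30% dull; felt feet given random scores 1-10; the share of DN-present patients with only one insensate foot set at 0, 0.5 or 1; two feet summarised as the lower score, as the mean, or analysed per foot. The table gives the range of rejection over these settings, 500 runs each, N = 139.

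| Prevalence | Mann-Whitney | Kruskal-Wallis |
|---|---|---|
| 3% | 67-100% | 59-98% |
| 5% | 92-100% | 88-100% |
| 10% | 99.4-100% | 98.8-100% |
| 20% | 100% | 100% |

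At N = 552 and 10% prevalence (half one-foot cases, lower score) both tests rejected in all 200 runs.

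**Absent left blank, 10% prevalence, N = 139.**

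- All DN-present patients insensate in both feet: that group has no scores, so the Mann-Whitney cannot be run. The Kruskal-Wallis becomes dull v sharp and rejects in 4-7%.
- Half or all of them one-foot cases: the Mann-Whitney rejects in about 5-53% and the Kruskal-Wallis in about 4-43%, depending on the two-foot summary.

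The high end arises with the lower-score summary. A one-foot patient then supplies a single random score (mean 5.5), while others supply the lower of two (mean (1² + 2² + … + 10²)/100 = 3.85). The spurious difference thus makes DN-present patients look more sensitive.

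**Comparisons not built on absence.** With random scores, dull v sharp alone (38 v 87) rejects in 4.3% of 4,000 runs, and grouping by an unrelated 10% positive result rejects in 4.4%. Both are close to 5%, so removing the circular grouping removes the artefact.

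**The case against.** Several points on the other side are fair.

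- The protocol speaks of feasibility, lists descriptive statistics first and rests no decision on these p-values. A reader might infer that a validation claim is planned; the text does not say so. But it ties the scale to the degree of neuropathy, and these are the only tests it names for that.
- A reader might infer that the tests cannot fail. The documents do not support that. The form is the only instruction on recording a score for an absent foot, and it points to a blank, under which the Mann-Whitney is uncomputable or arbitrary rather than automatically significant. One-foot cases also dilute the effect at low prevalence.
- Within the Kruskal-Wallis, dull v sharp is not forced: both have sensation, and Table 6 does not separate them by score. Only the no-sensation group is circular.
- A reader might infer that each patient will be counted twice. Nothing says that feet will be analysed as separate observations, and Table 6 classifies patients.
- Coding and two-foot summaries can be left to a statistical analysis plan. That stands, but the tests and their groups are fixed in the protocol, and neither coding rescues them.

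One could also argue that the yes/no groups are monofilament groups, which would not be circular. The surrounding sentences discuss only Medipin readings, and the monofilament enters in the next paragraph. If monofilament groups are meant, the section must say so.

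**Conclusion.** The point holds as a should-fix on a secondary objective. The Mann-Whitney test, and the no-sensation part of the Kruskal-Wallis, compare the score with groups made from the same answer and cannot show that the scale grades neuropathy.

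The size depends on coding. With absent = 0, random scores are significant in about 99-100% of studies at 139 patients and 10% prevalence, falling to 67% (Mann-Whitney) and 59% (Kruskal-Wallis) in the least favourable settings at 3%. With absent = blank, the Mann-Whitney ranges from impossible to a false-positive rate of about 53%, according to a summary rule that the protocol does not give. These figures rest on the simulation assumptions listed above; the circularity itself rests only on section 5.3, Table 6 and section 8.4.

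The kappa and McNemar analyses and the sample size do not use these tests. The detection rates are touched only through the unclassified case of a foot felt but scored 0.

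**What to change.** 1. Drop the Mann-Whitney test against Medipin's own yes/no result, and drop the no-sensation group from the Kruskal-Wallis. Show the score by category descriptively.
2. State one score per patient (for example, the lower of the two feet), how an absent foot is coded, and how a patient with one dull and one sharp foot is classed.
3. Among patients with sensation in both feet, compare the score between dull and sharp. The coding of absent feet does not affect this comparison. Read it as internal consistency, since both are answers to the same stimulus.
4. In the same patients, report the Spearman correlation of the score with the MNSI small-fibre count. Appendix 4 supplies the items: "Questions 2, 3, 5, 6, 7, and 14 are considered indicators of small fibre nerve dysfunction", with item 7 reverse-scored. With about 125 patients, a 95% interval around a correlation near zero is roughly ±1.96/√122 = ±0.18.
5. Treat correlations with the dorsal and plantar monofilament totals as supplementary. The protocol holds that the devices test different fibres, so a null result there would not show that the scale fails.
6. Reconcile Table 6 so that a foot felt but scored 0 falls into one class.

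**Cost.** Items 1 to 5 are rewording of section 8.4 and a coding note for the form; no new measurement is needed. The form itself records only whether the MNSI was completed, so item answers must be entered from the questionnaire. Item 6 changes a primary-outcome definition and should be settled before results are examined.

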#### Medipin test: one application on dorsal side of hallux, proximal to toenail, on both left and right foot

1. Break tab to expose point - avoid contact with fingers.

2. Grasp device between thumb and index finger lightly enough to permit slight axial slippage if required - utilize textured surface to facilitate control.

3. Apply to skin at a perpendicular to standardize point pressure for improved test consistency and optimize annular contact to generate a 'centre surround' field of enhanced acuity. Establish a control area in an unaffected region (forearm) with an 'average' stimulation level by making several quick applications around the same locality for about 5-10 seconds. Press firmly but carefully using a repetitive, percussive contact.

Avoid high amplitude or 'stabbing' actions - penetration is checked by the annulus but never assumed 'impossible'. Instruct your patient this "normal" area represents a 'sharp' sensation and that this equates to a score of 5 out of 10 (on a 10cm scale).

4. With patient's eyes closed, apply the Medipin once to the dorsal area of the great proximal to the nail bed. Ask patient where possible to identify and grade the quantity of deficit between them and the 'control' area. Answer can be no sensation, 'dull' sensation, and 'sharp' sensation. Patient will also score the sensation on a 10cm visual analogue scale.

5. To prevent re-use destroy point by compression against a hard surface and/or dispose of in a biohazard container.

Figure 2. Medipin device.

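### The rank tests on the Medipin score (8.4) have no defined patient-level unit, include a no-sensation group that is 0 or empty by construction, and do not test medians

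*Protocol*

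**What the plan says.** **Recording.** Section 5.3 describes the "Medipin test: one application on dorsal side of hallux, proximal to toenail, on both left and right foot". After each application the patient answers none, dull or sharp, and "Patient will also score the sensation on a 10cm visual analogue scale". The case report form (Appendix 1) has separate left and right entries for category and score, the score being headed "Score if sensation felt (5 being forearm reference score").

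**Patient-level rule.** Table 6 in section 8.3 counts neuropathy as present on Medipin when there is "No sensation in one or" both feet. It counts neuropathy as absent only when both feet have sensation with a score above 0. Nothing assigns a patient one of three categories or a single score.

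**Tests.** Section 8.4 says the "Mann-Whitney U-test will be used to compare median 10-point score between those with present and absent DN respectively", "to determine if the median value differs", and then that the "Kruskall-Wallis test will be used to compare median score between the three groups of no sensation/dull sensation/sharp sensation". Section 8 closes by saying that "inferential statistics will be performed on pooled data". The documents give no significance level and no between-foot correlation.

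**The concern.** A patient who answers sharp on one foot and dull on the other belongs to no defined group of the three-group test. The foot is the only unit with both a category and a score. Two feet of one person are likely to be alike in both, and Kruskal-Wallis assumes independent observations. For the Mann-Whitney test the groups are patients but the scores are per foot, and no text says which score represents the patient.

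Two further problems do not depend on the unit. The no-sensation group cannot have an ordinary score. And both tests are described as comparing medians, which is not their null hypothesis.

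These are the only inferential tests that section 8.4 names for the objective of showing that a 10-point scale is workable. A small p-value could be reported as evidence that the scale grades neuropathy when it reflects double counting, or the way the score is recorded.

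**Working it through.** **1. Inputs.** From section 8.2: 10% prevalence, 95% confidence, 5% precision, population 160,000.
- n0 = 1.96² × 0.1 × 0.9 / 0.05² = 138.29. With finite population correction: 138.29 / (1 + 137.29/160000) = 138.17, so 139 as stated.
- For 2.5% precision: 553.17, corrected to 551.27, so 552 as stated.
- Hence 139 patients and 2 × 139 = 278 feet. At 10% prevalence about 14 patients are positive and 125 negative.

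Assumed because the protocol is silent: 5% two-sided level, category shares, score distribution, between-foot correlations.

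**2. Feet analysed as independent.** Simulation of 139 patients × 2 feet, score unrelated to category, shares 10/30/60% (absent/dull/sharp), the same latent between-foot correlation for score and category, 3,000 runs each:

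| Correlation | Kruskal-Wallis on 278 feet |
|---|---|
| 0 | 5.0% |
| 0.5 | 6.8% |
| 0.7 | 9.4% |
| 0.8 | 11.1% |
| 0.9 | 13.8% |

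The Monte Carlo standard error is √(0.05 × 0.95/3000) = 0.4 points at 5%. This null gives absent feet ordinary scores, which real data cannot do (step 4). For dull versus sharp alone the rates are 9.0% at 0.8 and 10.7% at 0.9.

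Varying the two correlations separately (shares 10/25/65%, 2,500 runs), three groups / dull versus sharp only:

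| Score correlation | Category 0 | Category 0.6 | Category 0.8 | Feet always share category |
|---|---|---|---|---|
| 0.3 | 4.2 / 4.9% | 6.3 / 5.5% | 6.4 / 6.0% | 9.3 / 8.1% |
| 0.5 | 5.1 / 5.2% | 7.4 / 7.1% | 8.6 / 7.4% | 12.9 / 9.9% |
| 0.7 | 4.8 / 5.3% | 8.8 / 6.3% | 10.1 / 7.8% | 17.0 / 13.4% |
| 0.9 | 5.2 / 4.8% | 8.9 / 6.8% | 13.2 / 9.6% | 19.2 / 15.0% |

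There is no inflation when category is uncorrelated between feet. A larger trial does not help: with 552 patients and both correlations 0.8, the rate is 11%.

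**3. Analytic check.** With design effect DE, the rejection rate on 2 degrees of freedom is P(χ² > 5.99/DE) = 0.05^(1/DE). When both feet share a category, DE is about 1 + score correlation: 1.3 gives 10.0%, 1.5 gives 13.6%, 1.7 gives 17.2%, 1.9 gives 20.7%. These lie close to the last column (9.3, 12.9, 17.0, 19.2%).

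**4. Circularity.** Suppose k of N records have no sensation and score 0, all others score above 0, and dull and sharp have equal mean ranks. The zeros have mean rank (k+1)/2 and the rest (N+k+1)/2. Then, before tie correction (which only raises it),

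H = 12/[N(N+1)] × [k((N−k)/2)² + (N−k)(k/2)²] = 3k(N−k)/(N+1).

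With N = 139, k = 14: H = 3 × 14 × 125/140 = 37.5, against a critical value of 5.99. With k = 3: H = 3 × 3 × 136/140 = 8.7, still significant. A simulation at patient level with 10% zeros and identical dull and sharp distributions rejected in 100% of runs. If absent feet have no score instead, that group is empty and only dull versus sharp remains. The Mann-Whitney test shares the problem, because every patient in its positive group has at least one foot without sensation.

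**5. Medians.** Let X = E1 − ln 2 and Y = ln 2 − E2, with E1 and E2 independent standard exponentials. Both medians are 0, yet P(X > Y) = P(E1 + E2 > 2 ln 2) = e^(−1.386) × (1 + 1.386) = 0.25 × 2.386 = 0.60. Mann-Whitney rejects in 22% of runs at 14 versus 125 and in 52% at 70 versus 69. Another pair of skewed 0–10 distributions sharing median 5 gave 90% at 14 versus 125. The size depends on shape; the principle does not.

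**6. Candidate repairs under the null.**
- Worst-foot category with the mean of the two scores: 4.7%. Left foot only: 4.4% (both at correlations of 0.8).
- Worst-foot category with that foot's own score, or the lower score when both feet share the category: about 29–32% at correlation 0.5 and 10–11% at 0.8. Sharp patients always contribute the smaller of two scores, while mixed patients contribute a single one.

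**The case against.** A reader might infer that the protocol treats 278 feet as independent. It does not say so. Section 8.4 leaves the unit open. The Mann-Whitney groups are defined by patient through a worst-foot rule, and the Kruskal-Wallis test is introduced as a parallel analysis, so a patient-level reading is available. The closing remark on pooled data follows a statement about per-protocol analysis and loss to follow-up, and is too vague to prove that feet are pooled. So it is also wrong to say that the test can only be run on feet: a patient-level test is possible once a rule is written.

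A reader might also infer that the false-positive rate doubles. That needs correlations near 0.8 in both score and category. At 0.5 the rate is about 7%, and with uncorrelated categories there is no inflation.

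It can further be said that the choice of foot is a detail for a statistical analysis plan, and that 8.4 puts descriptive statistics first. Both points reduce the weight of the unit problem. They do not remove it, because section 8 presents itself as the data analysis plan and names a test whose inputs exist only per foot. They do not touch the circularity or the reference to medians, which stand whatever the unit.

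**Conclusion.** The point holds in a limited form. The unit and the score rule for the two rank tests are undefined at patient level. If feet are entered as they are recorded, the three-group test rejects a true null in about 5% to 14% of trials for equal between-foot correlations of 0 to 0.9 (up to 19% in the extreme case where both feet always share a category). For the informative contrast, dull versus sharp, it is 9.0% at 0.8 and 10.7% at 0.9. These figures rest on assumed correlations, category shares and score distributions.

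The circularity is the more serious flaw and needs fewer assumptions. If absent sensation is scored 0, three such records among 139 are enough for significance even when dull and sharp do not differ. The stated aim of detecting a difference in medians is not what either test delivers without a shift assumption, and that assumption fails when one group is fixed at 0.

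The effect is confined to the secondary 10-point-scale objective. The detection rates and the sample size, which reproduces as 139 and 552, are unaffected.

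**What to change.** In section 8.4:

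1. **State the unit.** Either keep feet and use a patient-clustered analysis (GEE, or a permutation that moves both feet of a patient together), or form one record per patient: worst-foot category with the mean of the two scores, or one prespecified foot. Do not use the worst foot's own score or the lower score (step 6 of the working).
2. **Limit inference to dull versus sharp.** Describe the no-sensation group only, and present the score by neuropathy status descriptively for the same reason. State whether an absent foot is recorded as 0 or left blank; section 5.3 and the case report form should agree on this.
3. **Reword the conclusion.** Replace the reference to medians by a difference in distributions, reported as U/(n1 × n2), the probability that a score in one group exceeds one in the other (ties counted as half), with a 95% confidence interval. If feet are the unit, the interval must allow for clustering.

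This costs a few lines and no new data. The one-record version with mean score lets a sharp foot's score dilute the dull group, and leaves out the felt foot of a patient whose other foot is absent. The clustered version keeps those feet and is preferable if it can be run.

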#### 8.2 SAMPLE SIZE CALCULATION

Since Medipin and monofilament do not assess the same nerve types, a true concordance study cannot be conducted. Hence a sample size is calculated for the prevalence of diabetic neuropathy being present. For the sake of a sample size calculation the assumption is that both tests will detect diabetic neuropathy in a conservative 10% of the sampled population. In the literature a ~20% prevalence of diabetic neuropathy in diabetics is reported but many of these reports are from nearly 30 years ago and therefore a more modest percentage is assumed here. Since it is not expected that the concordance will be high due to the different fibres being tested, calculation of a sample size with sufficient power based on a hypothetical concordance rate is not included here.

Using an online calculator, https://sampsize.sourceforge.net/iface/, with the predetermined criteria of a population of 160,000, 95% confidence interval, and precision of 5%, the required sample size is 139 patients.

Subject to submission of an amendment and appraisal of how patient recruitment into the initial cohort fares, we would like to extend the study to detect 2.5% precision. Again assuming 10% prevalence (which will be reviewed once initial 139 patients have been recruited), 95% confidence interval, and the stricter 2.5% precision, a revised new total of 552 patients will be required.

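### The devices' detection rates are formally compared only by a McNemar p-value, with no paired difference or interval, and the 139-patient sample size describes a single rate rather than that difference

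*Protocol*

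**What the plan says.** Protocol 2.1 makes the respective detection rates of Medipin and the 10g monofilament the primary objective. Table 5 in 5.2 has every participant undergo all three procedures (plantar monofilament, dorsal monofilament, Medipin) at one visit, so the data are paired.

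- **Primary analysis (8.3).** The results "will be presented with descriptive statistics to show percentage of patients with LOPS / DN". No interval or comparison is named.
- **Secondary analysis (8.4).** Cohen's kappa is assigned to agreement. For the rates, "McNemar's test for paired data will be used to compare distribution of outcomes between Medipin and each 10g monofilament procedure outcome". For plantar against dorsal monofilament, "the same test is conducted to compare the two different 10g monofilament diagnostic test procedures". The only intervals named are for odds ratios from an optional logistic regression.
- **Sample size (8.2).** For planning, "the assumption is that both tests will detect diabetic neuropathy in a conservative 10% of the sampled population". With a finite population of 160,000, "95% confidence interval, and precision of 5%, the required sample size is 139 patients". A possible extension uses the "stricter 2.5% precision, a revised new total of 552 patients will be required". The section says openly that no power calculation based on concordance was made, and that high concordance is not expected because the devices test different fibres.

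**The concern.** The question is comparative and paired, yet the plan gives a percentage for each test and a p-value for the comparison, and nothing that shows how large a difference the data leave open. A McNemar p-value above 0.05 cannot separate similar detection rates from too few discordant pairs.

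The sample size does not fill the gap. The ±5 and ±2.5 points describe one rate. The precision of a paired difference is governed by the proportion of patients on whom the two tests disagree, which 8.2 does not quantify. Low concordance between Medipin and monofilament, which 8.2 expects, means more discordant pairs and a less precise difference.

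At stake is the main message of the report. A difference of half the assumed prevalence could remain compatible with the data while the only formal result is a non-significant test. The decision on extending to 552 would likewise rest on single-rate precision.

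**Working it through.** **Inputs from the protocol (8.2):** n = 139, possible extension to 552; 10% positive on each test; 95% confidence (z = 1.96); precision 5 or 2.5 points; population 160,000.

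**Assumptions, not in the protocol:** two-sided 5% McNemar test; true rates of 10% and 15% as the example; overlap between tests from independence to complete. Overlap means the share of patients positive on the lower-rate test who are also positive on the other.

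**1. The plan's own figures.** n0 = z² p(1−p)/d², then n = n0 / (1 + (n0 − 1)/160,000).
- d = 0.05: n0 = 3.8416 × 0.09 / 0.0025 = 138.3; corrected 138.2, so 139.
- d = 0.025: n0 = 3.8416 × 0.09 / 0.000625 = 553.2; corrected 551.3, so 552.

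Both reproduce. The formula contains one proportion and no term for a second test.

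**2. Precision of the paired difference.** With both rates at 10%, the expected difference is zero and the 95% half-width is 1.96 × √(discordant proportion / n). Under independence the discordant proportion is 2 × 0.10 × 0.90 = 0.18. A discordance of 0.10 serves as a higher-agreement case.

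| Discordant | n = 139 | n = 552 |
|---|---|---|
| 10% | 1.96 × √(0.10/139) = ±5.3 points | ±2.6 points |
| 18% | 1.96 × √(0.18/139) = ±7.1 points | ±3.5 points |
| Single rate, as in 8.2 | ±5.0 points | ±2.5 points |

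**3. Power of McNemar's test at n = 139, 10% against 15%.** Discordant proportion = 0.10 + 0.15 − 2 × (proportion positive on both). Power is summed over the binomial number of discordant pairs and over their split.

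| Overlap | Positive on both | Discordant | Exact test | Uncorrected chi-square |
|---|---|---|---|---|
| Independent | 1.5% | 22% | 18% | 25% |
| Half | 5% | 15% | 26% | 34% |
| 80% | 8% | 9% | 41% | 50% |
| Complete | 10% | 5% | 70% | 92% |

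From independence to 80% overlap, the exact test misses the 5-point difference 59-82% of the time and the uncorrected test 50-75%. At complete overlap the miss rates are 30% and 8%.

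**4. A larger difference, 10% against 20%, exact test, n = 139:** power 59% (independent), 71% (half overlap), 89% (80% overlap).

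**5. What the interval would add.** Suppose 19 patients are positive on Medipin only and 12 on monofilament only. Exact McNemar gives p = 0.28. The difference is (19 − 12)/139 = 5.0 points. Its Wald half-width is 1.96 × √(31 − 7²/139)/139 = 7.8 points, so the 95% interval runs from about −2.8 to +12.8 points. The interval shows that differences above 12 points are not excluded; the p-value does not.

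**The case against.** The strongest reply is that the protocol never treats a non-significant result as equality. It sets no margin and no equivalence aim. The common 10% is a device for the sample size, and 2.2 and 8.2 argue that the devices measure different things. That is correct. A reader might infer that non-significance is the outcome planned for, or that the report will claim equal detection; the text supports neither. It is a risk of interpretation.

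Three further points stand. First, 8.4 gives agreement to kappa and the comparison of distributions to McNemar, which is the proper use of each, so it would be wrong to say that McNemar is the plan's measure of concordance between Medipin and monofilament. Second, the point difference can be read off the percentages in 8.3; only its uncertainty is missing. Third, 8.2 discloses that no concordance-based power calculation was made, so low power contradicts nothing in the document.

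The power figures also depend on assumed rates, overlap and test version. The expectation of low concordance rests on different fibres being tested. It does not extend to plantar against dorsal monofilament, which use one device and may overlap far more.

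It can also be said that interval methods are usually left to a statistical analysis plan, which is not shown here. That has force for the choice of formula. It has less for the choice of result: section 8 is headed as the data analysis plan, names its tests and software, and selects a p-value as the sole formal comparison on the primary question.

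**Conclusion.** The point holds as a weakness in the chosen analysis. The formal comparison of detection rates is a p-value with no paired difference or interval, and the stated precision belongs to a single rate.

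On the assumptions shown, 139 patients give about 18-41% exact power for 10% against 15% from independence to 80% overlap, and about 70% at complete overlap. With both rates at 10% and 10-18% discordance, the difference is known to about ±5.3 to ±7.1 points at 139 and ±2.6 to ±3.5 at 552. The protocol gives no discordance figure, alpha or target difference, so none of these should be quoted without its assumptions. In particular, ±7.1 and ±3.5 require full independence; the protocol says only that high concordance is not expected.

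The sample sizes themselves are correctly calculated for their stated purpose.

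**What to change.** - **8.3:** report the paired difference in detection rate with a 95% confidence interval for paired proportions (for example Newcombe or Tango), for Medipin minus plantar monofilament and for Medipin minus dorsal monofilament.
- **8.4:** do the same for plantar minus dorsal monofilament. Keep McNemar's test as a supporting p-value and kappa for agreement. State that p > 0.05 will not be interpreted as equal detection.
- **8.2:** state that ±5 and ±2.5 points apply to each single rate, and that the precision of a difference depends on the discordant proportion. The ranges in the verdict can be given, labelled as assumptions. The observed discordance in the first 139 patients can then inform the decision on extension.

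The cost is a few sentences and one standard calculation on data already collected. No patients, visits or tests are added. The precision stated for the comparison becomes somewhat less favourable than the figures now in 8.2.
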